5. TREATMENTS

5.1 Identity of Study Treatment

All study drugs will be labeled consistent with the requirements of local law and legislation. Label text will be approved consistent with the sponsor's agreed procedures, and a copy of the labels will be made available to the study site upon request.

For all study drugs, a system of numbering in accordance with all requirements of Good Manufacturing Practice (GMP) will be used, ensuring that each dose of study drug can be traced back to the respective bulk batch of the ingredients. Lists linking all numbering levels will be maintained by the sponsor's clinical supplies quality assurance group.

A complete record of batch numbers and expiry dates of all study treatment as well as the labels will be maintained in the sponsor's study file.

5.2 Dosage and Administration

PCLX-001 will be provided as an oral daily dose on a 28-day cycle. Doses should be taken around the same time each day, within a ± 3 hour window. PCLX-001 capsule(s) are to be taken by mouth and swallowed with approximately 250 ml of water, at least ninety minutes after eating solid food. After PCLX-001 is taken, the patient should wait 2 hours before eating solid food. Missed doses for any reason (i.e. outside of the allowable dosing window) will not be administered at a later time. In Part A, dose-escalation levels are provided in Section 3.3. PCLX-001 capsules are available in doses of 10 mg and 70 mg and the number of capsules will be calculated to ensure proper daily dosing is provided.

5.3 Dose Delay and Modifications

Dose adjustments are to be made according to the organ system showing the greatest degree of toxicity. Toxicity will be graded using the National Cancer Institute Common Terminology Criteria for Adverse Events (NCI CTCAE, Version 5.0).

5.3.1 Cycle 1 DLT Modifications for Part A Dose-Escalation Cohorts

If a patient experiences a treatment related hematological or non-hematological DLT (as defined in Section 3.2) during Cycle 1, the next dose of PCLX-001 will be delayed for up to 28 days for Part A. If the toxicity fails to resolve to CTCAE Grade ≤ 2 within 28 days, the patient should be withdrawn from study treatment but followed for safety until resolution.

If the toxicity resolves to CTCAE Grade ≤ 2 , re-treatment with PCLX-001 can be considered. Re-treatment of this patient should be at 1 dose level below the initial dose. Detailed dose modifications are described in Table 5-1. Patients experiencing any drug-related, clinically significant, non-hematological CTCAE Grade 4 toxicity will be withdrawn from study treatment but followed for safety until resolution. There will be no intrapatient dose escalation and no more than two dose reductions will be allowed.

Table 5-1: Dose Modifications of PCLX-001

Existing Dose (mg)	Modified Dose (mg)
280	210
210	140
140	100
100	70
70	40
40	20
20	10
10	Discontinue study drug

5.3.2 Dose Modifications for HEMATOLOGIC Toxicities

For cycle 2 and beyond, Day 1 administration of PCLX-001 requires a platelet count of $\geq 75 \times 10^9/L$ and an absolute neutrophil count (ANC) of $\geq 1.5 \times 10^9/L$. CBC's drawn within 72 hours of treatment day may be used provided they meet parameters. However, if treatment parameters are not met, dose interruption will be made on the basis of blood counts taken the day of scheduled treatment. If counts are below this threshold, treatment will be delayed for 1 week and reassessed weekly until these parameters are met.

If a patient experiences a hematologic DLT in the preceding cycle OR if treatment is held for > 7 days due to neutropenia and/or thrombocytopenia, then the subsequent cycle will be administered at one lower dosing level. No more than two dose reductions will be allowed.

Patients should not receive prophylactic G-CSF for cycle 1. Subsequent use will be at the discretion of the treating physician and as per the ASCO guidelines on colony stimulating factors.

5.3.3 Dose Modifications for NON-HEMATOLOGIC Toxicities

For a Grade ≥ 3 non-hematological toxicity considered to be clinically significant and attributed to PCLX-001, treatment will be delayed for up to a maximum of 28 days. If the toxicity resolves to CTCAE Grade ≤ 2 , the next dose of PCLX-001 can be considered at 1 lower dose level (Table 5-2). Grade 4 clinically significant toxicities related to PCLX-001 will result in discontinuation of PCLX-001.

There will be no intrapatient dose escalation and no more than two dose reductions will be allowed.

Table 5–2: Non-hematological Criteria for Dose Delay and Dose Modification

CTCAE	Dose delay	Dose modification
Grade^a		
0 – 2	Treat on time	No change
3	Delay ^b until CTCAE Grade ≤2	Decrease 1 dose level ^c
4	Discontinue permanently	Discontinue permanently

^a Excludes alopecia, non-refractory nausea/vomiting, and non-refractory diarrhea. For TLS see Table 5-3

^b If no recovery after 28-day delay, PCLX-001 treatment will be discontinued.

^c Dose will not be re-escalated after reduction for toxicity. If more than 2 dose reductions are required, treatment will be discontinued.

Gastrointestinal Events

Diarrhea: No prophylactic treatment for diarrhea is recommended. Anti-diarrheals can be used when needed. A further dose of study medication should not be given before treatment related diarrhea has recovered to CTCAE Grade ≤ 2.

Nausea/Vomiting: No prophylactic treatments for nausea or vomiting are recommended, but anti-emetic drugs can be used when needed. A further dose of study medication should not be given before treatment related nausea/vomiting has recovered to CTCAE Grade ≤2.

Constipation: Patients can continue laxative as concomitant medication, but start of prophylactic treatments before study drug is administered is not recommended. Laxative can be used when needed.

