3.2 Definition of Dose Limiting Toxicity and Maximum Tolerated Dose

Toxicities are to be graded according to the National Cancer Institute Common Terminology Criteria for Adverse Events (NCI CTCAE, Version 5.0). A copy of the CTCAE version 5.0 can be downloaded from the CTEP home page (<http://ctep.cancer.gov>).

Dose Limiting Toxicity (DLT) for Part A, dose-escalation, is defined as any of the following AEs related to PCLX-001 treatment occurring in Cycle 1:

Hematologic

- Grade 4 thrombocytopenia (platelet count < 25 x 10⁹/L)
- Grade ≥ 3 thrombocytopenia (platelet count < 50 x 10⁹/L) associated with any major bleeding, and/or requirement for transfusion
- Grade 4 neutropenia (ANC < 0.5 x 10⁹/L) for ≥ 7 days^a
- Febrile neutropenia. (Per NCI CTCAE, ANC < 1.0 x 10⁹/L and fever ≥ 38.3°C or a

sustained temperature of $\geq 38^{\circ}\text{C}$ for more than one hour). Febrile neutropenia is by definition a grade ≥ 3 toxicity.

^a Detection of CTCAE Grade 4 neutropenia (only in Cycle 1) will trigger twice-weekly white blood cell counts to be performed, and will be considered a DLT if drug interruption lasts ≥ 7 days.

Non-hematologic

Any non-hematological toxicity of CTCAE Grade ≥ 3 is considered a DLT, excluding the following:

- Grade ≥ 3 nausea, vomiting and diarrhea which are controlled with anti-emetics and/or other supportive care within $\leq 72\text{hr}$
- Brief (i.e. lasting ≤ 72 hours) CTCAE Grade 3 fatigue
- Alopecia of any grade
- Isolated, asymptomatic, biochemical laboratory values including electrolyte abnormalities, above or below normal reference ranges, which are judged not clinically significant by the Investigator
- Miscellaneous
- Any patient meeting Hy's law of drug-induced hepatic injury (AST or ALT >3 times ULN with bilirubin 2 times ULN; absence of initial cholestasis with ALP >2 times ULN; no other explanation) is considered a DLT.
- Any toxicity thought to be related to study drug that, at the discretion of the investigator, or his/her designated associate(s), is thought to warrant withholding the drug may be declared as a DLT. Such toxicities might for example be CTCAE Grade 1 or CTCAE Grade 2 toxicities that interfere with the activities of daily life, such as long-lasting fatigue, or anorexia, making a dose reduction necessary in order to ensure the patient's compliance.

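### Outside Part A Cycle 1 no dosing rule covers Hy's law, so Table 5-2 can direct full-dose treatment of a patient who meets it

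*Combined protocol and SAP*

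**What the plan says.** Section 3.2 lists "Any patient meeting Hy's law of drug-induced hepatic injury" as a DLT: AST or ALT above 3 times ULN with bilirubin at 2 times ULN, plus "absence of initial cholestasis with ALP >2 times ULN; no other explanation". The list has a limited scope: "Dose Limiting Toxicity (DLT) for Part A, dose-escalation, is defined as any of the following AEs", and only events in Cycle 1 count. Section 5.3.1 attaches a hold of up to 28 days to those DLTs. Re-treatment one level lower can be considered once the toxicity is Grade 2 or less.

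All other non-hematologic dosing falls under Section 5.3.3. For a Grade 3 or higher toxicity "considered to be clinically significant and attributed to PCLX-001, treatment will be delayed for up to a maximum of 28 days", with a one-level reduction on recovery to Grade 2 or less. Clinically significant, related Grade 4 toxicity ends treatment. Table 5-2 has Grades 0 to 2 dosed on time without change. Footnote a states: "Excludes alopecia, non-refractory nausea/vomiting, and non-refractory diarrhea. For TLS see Table 5-3".

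Two neighbouring rules matter. Section 5.3 says "Dose adjustments are to be made according to the organ system showing the greatest degree of toxicity". Section 5.3.2 sets a blood-count gate: "For cycle 2 and beyond, Day 1 administration of PCLX-001 requires a platelet count of" at least 75 × 10⁹/L and an ANC of at least 1.5 × 10⁹/L. If the counts are too low, "treatment will be delayed for 1 week and reassessed weekly until these parameters are met". There is no such gate for liver tests. The only other liver limits are for entry: exclusion 7 bars bilirubin ≥1.5 times ULN, and ALT and AST ≥3 times ULN (≥5 times with malignant liver involvement).

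**The concern.** Hy's law is a combination: two moderate abnormalities together signal a risk that neither shows alone. A table that works by grade cannot see the combination, and Section 5.3 directs attention to the worst organ system, not to how two values combine. The same laboratory picture is therefore dose-limiting in Part A Cycle 1, yet triggers no specific action one cycle later or in any of the 40 Part B patients.

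Two consequences follow if Grade 2 reaches far enough. A Hy's law case that is Grade 2 on both values is directed to continue at full dose. A case that starts at Grade 3 is held, but can satisfy the recovery test and be re-treated one level lower while Hy's law is still met. In either situation the patient's bilirubin is above the level that would have barred entry (2 against 1.5 times ULN).

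**Working it through.** **Scope.** Reading across Sections 3.2, 3.6, 5.3.1 to 5.3.3, 5.4 and 10.5, Hy's law appears only in Section 3.2. No on-treatment rule combines transaminases and bilirubin. This needs no assumption.

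**Can a Hy's law case be Grade 2?** Let A be ALT or AST, B bilirubin and P ALP, all as multiples of ULN, with no other explanation for the injury. Hy's law in Section 3.2 is A > 3, B at 2, and not P > 2. The text gives no inequality sign for bilirubin, so both B ≥ 2 and B > 2 are checked. The protocol grades by CTCAE v5.0 but does not print the cut-offs. Assumption, for a normal baseline: Grade 2 is A > 3 to 5 and B > 1.5 to 3. Then A between 3 and 5 with B between 2 and 3 is both Grade 2 and Hy's law.

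| A / B / P | Table 5-2 action | Hy's law met? |
|---|---|---|
| 4 / 2.2 / 1.2 | Grade 2: full dose continues | Yes |
| 6 / 2.2 / 1.2, falling to 4.8 / 2.2 / 1.2 | Grade 3: held, then counts as recovered | Yes, at both points |
| 4 / 3.5 / 1.2, falling to 4 / 2.8 / 1.2 | Grade 3: held, then counts as recovered | Yes, at both points |

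The hold in the last two rows also requires that the event be judged clinically significant and attributed to the drug. In Part A Cycle 1, a Grade 2 Hy's law DLT is held under Section 5.3.1 but already satisfies that section's Grade ≤2 re-treatment test at onset.

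**Boundary check.** Take A in {3.5, 4, 5, 6, 8, 12}, B in {2, 2.2, 3, 3.5, 5} and P in {1.2, 2.0, 2.5}, which is 6 × 5 × 3 = 90 points. The 30 points with P = 2.5 fail Hy's law.

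- Reading B ≥ 2: 6 × 5 × 2 = 60 points meet it. Of these, 3 × 3 × 2 = 18 are Grade 2 and 42 are Grade 3.
- Reading B > 2: 6 × 4 × 2 = 48 points meet it. Of these, 3 × 2 × 2 = 12 are Grade 2 and 36 are Grade 3.

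This locates the gap; it says nothing about how often patients fall in it.

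**Sensitivity to the assumed cut-offs.** Let the Grade 2 upper limits be A in {3, 4, 5, 6} and B in {1.5, 2, 2.5, 3, 4}, which is 20 pairs. The gap exists when the A limit exceeds 3 and the B limit reaches Hy's bilirubin threshold: 3 × 4 = 12 pairs under B ≥ 2, and 3 × 3 = 9 under B > 2. It vanishes if Grade 2 ends at or below 3 times ULN for ALT/AST, or does not reach the bilirubin threshold.

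**Doses before the next scheduled chemistry (Table 7B).** Counting from the first dose:

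- Days 1, 8, 15, 22, 29: 7 doses between tests (the case that matters is Part B Cycle 1).
- Days 29, 43, 57: 14 doses (Cycle 2).
- Days 57, 85, 113: 28 doses (Cycle 3 onward).

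The visit window of ±2 days shifts these slightly.

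**The case against.** The strongest reply is that the harm depends on cut-offs the protocol does not print, and that clinicians would not follow the table blindly. Section 3.2 lets the investigator and sponsor modify or stop treatment for cumulative toxicity. Section 3.6 lists unacceptable adverse events and the physician's choice as reasons to stop, so stopping is not a deviation. Section 10.5 can halt accrual and call a meeting. A suspected drug-induced liver injury could be reported as an important medical event within 24 hours (Sections 9.3 and 9.3.1), unscheduled visits are allowed (Section 7.2), and a separate safety monitoring plan is to be set up (Section 10.3). Re-treatment after Grade 3 is optional. The nonclinical data do not point to the liver: mouse studies showed no hepatic toxicity, and dose-limiting toxicity in the GLP studies was attributed to gastrointestinal damage and reduced hematopoiesis.

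Much of this is fair. No frequency is known. The 7, 14 and 28 doses are a worst case in which nobody acts on a known abnormal result. The grade assumption is for a normal baseline, so patients entering with liver involvement and raised ALT/AST are not examined. But none of these clauses sets the dose for a Grade 2 Hy's law case, and Section 10.5 governs accrual, not that patient's drug. Nor does any of them stop the Grade ≤2 recovery test from being met while Hy's law persists. Section 3.2 also lists Hy's law separately from the Grade ≥3 rule. That suggests, without proving it, that lower-grade cases were foreseen. The sponsor gave TLS its own table instead of leaving it to discretion.

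**Conclusion.** The point holds and should be fixed. That Hy's law is absent from every dosing rule is a matter of text. That Table 5-2 then directs full-dose treatment, or permits re-treatment, during ongoing Hy's law rests on Grade 2 reaching above 3 times ULN for ALT/AST and up to the bilirubin threshold. Confidence is medium for that reason. The size is a patient-safety exposure of up to 28 daily doses between scheduled tests in an affected patient, in a first-in-human trial with no fixed end of treatment. The number of such patients cannot be estimated from the documents. DLT counts, escalation decisions and the MTD do not change.

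**What to change.** Add a separate line to footnote a of Table 5-2, alongside the TLS reference:

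> Hy's law as defined in Section 3.2, any cycle, Part A or Part B: hold PCLX-001 whatever the CTCAE grade and repeat chemistry weekly. Re-treat only one dose level lower, and only once bilirubin is <1.5 × ULN and ALT and AST are both <3 × ULN (<5 × ULN with malignant liver involvement). Discontinue if this is not reached within 28 days. Grade 4 remains permanent discontinuation, and the limit of two dose reductions still applies.

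In Section 5.3.1 add that, for a Hy's law DLT, this condition replaces Grade ≤2.

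The resume limits are those of exclusion 7. Using them during treatment is a judgement, and the sponsor could choose a stricter rule. The bilirubin limit must be met together with the transaminase limit, because <5 × ULN overlaps the Hy's law limb of >3 × ULN. At A / B of 2.9 / 1.4 or 4.9 / 1.4, Hy's law is no longer met under either reading, since B is below 2.

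The cost is one footnote line and one cross-reference in an amendment. A few patients would be held longer, and some who would have continued would stop at 28 days. Weekly chemistry means up to 28 / 7 = 4 draws per hold, mostly unscheduled from Cycle 3. Section 7.2 already allows such visits, and Section 5.3.2 already uses weekly reassessment for blood counts.

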5.4 Prophylaxis and Monitoring of Tumor Lysis Syndrome

Patients with high tumor burden and who are considered by the Investigator to be at risk for tumor lysis should receive tumor lysis prior prophylaxis prior to the initiation of treatment. Patients should be well-hydrated and maintain a fluid intake of approximately 2 L/day. In addition, patients should be treated with allopurinol 300 mg oral daily (or a suitable alternative as per institutional standard) ideally 24 - 48 hours prior to Cycle 1 Day of PCLX-001 treatment. Patient should continue to receive prophylaxis and adequate hydration as deemed appropriate by the Investigator to mitigate against tumour lysis syndrome (TLS).

The inherent risk of tumor lysis syndrome (TLS) is dependent on the malignancy being treated and individual participant characteristics. The risk of TLS with PCLX-001 in NHL patients is predicted to be highest for those with bulky disease (defined as any lesion > 10 cm on the screening CT scan) and elevated pretreatment lactate dehydrogenase levels, particularly in the presence of dehydration or compromised renal function. Whereas patients with DLBCL, MCL, and Burkitt lymphoma may be at higher risk of TLS compared to FL, any risk assessment based on tumor type must be considered along with the effectiveness of therapy. All patients should be assessed for the need for prophylaxis for TLS.

TLS is an emergency which requires immediate treatment. Balanced or isotonic solutions (without potassium) should be administered to ideally maintain urine output > 100 mL/h. Alkalization of the urine is not recommended in the treatment of TLS. In the absence of contraindications, patients with established TLS should be considered for rasburicase at a dose of 0.2 mg/kg/day or institutional standard. Intractable fluid overload, hyperkalemia, or reduced urine output in the setting of acute kidney injury should be assessed for the need for renal dialysis.

Dose modifications for TLS are summarized in Table 5-3.

Table 5–3: Tumor Lysis Syndrome Criteria for Dose Delay and Dose Modification

CTCAE	Dose delay	Dose modification
Grade		
3 or 4	Delay ^a until TLS resolved	Decrease 1 dose level ^b or discuss with Medical Monitor to reinitiate at target dose

^a If no recovery after 28-day delay, PCLX-001 treatment will be discontinued.

^b Dose will not be re-escalated after reduction for toxicity. If more than 2 dose reductions are required, treatment will be discontinued.

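### Section 5.3.1 and Table 5-3 contradict each other on a related, clinically significant Grade 4 tumour lysis syndrome in Part A Cycle 1

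*Combined protocol and SAP*

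**What the plan says.** Four places in the combined protocol and SAP bear on dosing after TLS.

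- **Section 5.3.1**, headed "5.3.1 Cycle 1 DLT Modifications for Part A Dose-Escalation Cohorts", says: "Patients experiencing any drug-related, clinically significant, non-hematological CTCAE Grade 4 toxicity will be withdrawn from study treatment". For a DLT that resolves to Grade 2 or lower, it says re-treatment can be considered and adds: "Re-treatment of this patient should be at 1 dose level below the initial dose". It refers the reader to Table 5-1 for the dose steps and does not mention TLS.
- **Section 5.3.3, running text**, is not limited to a part or cycle. It says: "Grade 4 clinically significant toxicities related to PCLX-001 will result in discontinuation of PCLX-001". TLS is not mentioned in that sentence.
- **Table 5-2, footnote a**, in the same section, qualifies the grade column: "Excludes alopecia, non-refractory nausea/vomiting, and non-refractory diarrhea. For TLS see Table 5-3".
- **Section 5.4** says: "Dose modifications for TLS are summarized in Table 5-3". That table has one row, for Grade 3 or 4. Treatment is held until TLS has resolved. The dose then goes down one level, "or discuss with Medical Monitor to reinitiate at target dose". Its footnotes require discontinuation only if there is no recovery after a 28-day delay or if more than two reductions would be needed.

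**The concern.** Under Section 5.3.1 a Grade 4 event that is related and clinically significant ends study treatment. Under Table 5-3 the same event, if it is TLS, ends treatment only on non-recovery or too many reductions; otherwise the patient may resume. Both texts apply to a Part A patient in Cycle 1, and the protocol states no order of precedence between them.

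What is at stake is consistent patient management. Section 5.4 describes TLS as an emergency and says that diffuse large B-cell, mantle cell and Burkitt lymphoma may carry a higher risk than follicular lymphoma. Section 4.1 admits all three higher-risk types to Part A. The study is multicentre, so two sites could each follow the protocol as they read it, one withdrawing the patient and the other seeking to resume.

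**Working it through.** No arithmetic on rates or power applies. The check sets the instructions side by side and asks whether anything in the documents decides between them.

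**1. Does a Cycle 1 TLS come under Section 5.3.1?** Section 3.2 makes related non-haematological toxicity of Grade 3 or higher in Cycle 1 a DLT unless it is on the exclusion list. TLS is not named there. Subject to that list, and to the documented review in Section 3.2 that can set an event aside, a related Grade 3 or 4 TLS in Part A Cycle 1 is a DLT and Section 5.3.1 applies.

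**2. Instructions by location.**

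| Location | Grade 3 TLS | Grade 4 TLS | TLS exception? |
|---|---|---|---|
| Section 5.3.1 (Part A Cycle 1 DLTs) | If resolved, re-treatment may be considered, one level lower | Withdraw, if related and clinically significant | None |
| Section 5.3.3 text | If resolved, next dose may be considered, one level lower | Discontinue, if related and clinically significant | None in the text |
| Table 5-2 with footnote a | Sent to Table 5-3 | Sent to Table 5-3 | Yes |
| Table 5-3 | Resume one level lower, or at target dose after discussion | Same as Grade 3 | It is the TLS table |

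**3. What this means at one dose.** Take a patient assigned 140 mg and read target dose as the assigned dose, which Table 5-3 does not define. Table 5-1 takes 140 mg down to 100 mg.

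- Grade 4: Section 5.3.1 gives withdrawal. Table 5-3 gives 100 mg, or 140 mg after discussion. The two sets of outcomes do not overlap.
- Grade 3: Section 5.3.1 gives 100 mg. Table 5-3 gives 100 mg, or 140 mg after discussion. The two agree on the first option and differ on the second.

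**4. Does another passage resolve it?** Footnote a belongs to Table 5-2 in Section 5.3.3, and Section 5.3.1 neither cites that table nor repeats the footnote. Section 3.4 says that after a DLT the dose is modified according to the protocol or the drug is stopped, but not which section governs. Section 10.5 holds accrual and calls a meeting for related serious or Grade 3 or higher unacceptable toxicity; that meeting decides whether enrolment reopens, not how the affected patient is dosed.

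**5. Does the DLT count change?** Sections 3.2 and 3.3 base escalation and the maximum tolerated dose on Cycle 1 DLTs. Section 3.4 makes a participant with a DLT evaluable regardless of days dosed, and Section 4.3 does not replace one who discontinues for a DLT. The patient counts as one DLT whether withdrawn, reduced or restarted.

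**The case against.** The strongest reply is that TLS was plainly meant to be handled separately. Footnote a redirects it, Section 5.4 names Table 5-3 as the place for its dose modifications, and a dedicated table would normally prevail over a general rule. At Grade 3, Section 5.3.1 uses advisory language and Table 5-3's first option matches it. Target-dose restart is open only after discussion with the Medical Monitor, and serious events are reported within 24 hours, so a site would not act unseen.

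Most of this stands. It largely answers the apparent conflict with Section 5.3.3, where only an unqualified sentence remains, and it makes the Grade 3 discrepancy minor. It does not answer the Grade 4 conflict with Section 5.3.1. That section is also specific, to one part and one cycle; it says *any* such toxicity and carries no redirect. A reader can defend either text as the controlling one.

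A reader might infer more than the documents support:

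- *That the contradiction covers every cycle and Part B.* Section 5.3.1 is confined to Part A Cycle 1 DLTs. Elsewhere footnote a leads to Table 5-3.
- *That Section 5.3.3 withdraws any related Grade 4 toxicity in the same terms.* The word *any* is in Section 5.3.1 only, and both rules require clinical significance.
- *That data at a dose level become uninterpretable, or that one case matters as 1/6 to 1/3 of a cohort.* The DLT count is the same under either instruction, and no planned analysis is shown to depend on post-DLT exposure.
- *That TLS is most likely in Cycle 1.* Section 5.4 times prophylaxis to before Cycle 1 dosing, but it relates risk to bulk, lactate dehydrogenase, hydration, renal function and histology, not to cycle.

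**Conclusion.** The point holds in limited form. There is one direct contradiction, withdraw against resume, for a related, clinically significant Grade 4 TLS in Part A Cycle 1. There is one lesser conflict, over the restart dose, for a Cycle 1 Grade 3 TLS that is a DLT. The Grade 4 sentence in Section 5.3.3 also omits an exception that its own table makes.

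The number of patients affected cannot be derived: the documents give no TLS rate and do not fix how many of the 9 to 52 Part A patients will have lymphoma. The consequence is inconsistent management of an emergency across sites, not bias in escalation or in the maximum tolerated dose. The conclusion assumes that TLS counts as non-haematological toxicity, as its treatment in Table 5-2 implies, and that the event is judged related and clinically significant. It takes no position on which instruction is clinically right.

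**What to change.** Reconcile Section 5.3.1, the Grade 4 sentence in Section 5.3.3 and Table 5-3 so that each TLS grade and cycle has a single instruction. If TLS is meant to be exempt from the general rule, write the exception and a reference to Table 5-3 into both sections. If it is not, change Table 5-3 to agree with them. The clinical choice belongs to the sponsor and the Medical Monitor.

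No new statement is needed that a Cycle 1 TLS can count as a DLT, because Section 3.2 already covers it and nothing ties DLT status to the restart decision. The cost is protocol wording only, with no change to sample size, assessments or analysis.
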